Study Protocol with SAP

A Randomized, Controlled Trial of a Telephone-Based Developmental Care Coordination System

NCT04118452

PI: [name] MD MS

Document Date: 3/28/2023

Abstract

Background

The American Academy of Pediatrics (AAP) recommends routine, universal developmental surveillance at all well-child visits for children from birth to 5 years old; universal screening with a structured, validated tool at the 9-, 18-, and 30-month visits; and Autism-specific screening at the 18- and 24-month visits. These recommendations are based on decades of research that demonstrate long-term benefits of high-quality early interventions. Despite these recommendations, only about 30% of pediatricians nationally conduct universal developmental screening, and children who screen positive often never receive formal evaluation or treatment until after kindergarten entry, when interventions may have less impact on long-term outcomes.

Multiple barriers prevent children with developmental risks from receiving services that might ultimately help them achieve optimal development. Beyond initial screening, children must be appropriately referred to service organizations, be evaluated by these organizations, be deemed eligible for services, and access these services. At every step along this series there is the potential for leakages, or “voltage drops.” Preliminary findings suggests that 2-1-1 Los Angeles County (211LA), part of the national 2-1-1 health and human services call center network, can address these barriers and reduce these voltage drops, connecting more children to services and potentially improving outcomes.

Objectives

This study examines: 1) the effectiveness of telephone-based early childhood developmental care coordination through 211LA in terms of rates of a) referral to evaluation by early intervention services, b) eligibility for early intervention services, and c) receipt of services, compared to usual care; 2) medium-term child developmental outcomes in the 211LA group, as determined by formal developmental assessment 2 years after enrollment, compared to usual care; and 3) the costs of 211-based care coordination, and also the potential long-term benefits in terms of improved educational, employment, and other outcomes.

Methods

The study design is a randomized controlled trial (RCT) of development-related care coordination through 211LA, compared to usual care, in community clinic populations. All intervention and control children will receive validated screening, which allows examination to focus comparisons on post-screening care coordination through 211LA vs. usual care.

We will aim to recruit 685 children ages 11-42 months—approximately 150-200 from each of four clinic systems – over approximately 16 months. The children will be individually randomized to usual care + 211LA + developmental screening results and usual care + developmental screening results. Based on our pilot trial, we expect to lose roughly 20% per year..

Participants

Potential subjects are identified through review of the Electronic Health Record in a two-stage process.

First, all clinic patients within the study age range (11-42 months), or who will be in study age range within 3 months, will be sent an Opt Out letter by each respective clinic. This process will be repeated every 3 months to identify new patients who have joined the clinic or aged into the study. This approach is being utilized to minimize time burden on the clinics as well as to allow the study to potentially include last minute / short notice appointments. This helps ensure that

families that do not schedule well child checks far in advance may still be able to be included in the study – avoiding systematic bias.

The Opt Out letter that will be sent by each clinic briefly describes the study and provides the study team's contact information so that potential participants can call to ask questions or opt out. This letter will also be available at the front desk at clinic sites to increase the reach of this highly mobile population

Second, the clinics will provide the Research team weekly to monthly with an appointment list of all potentially eligible children, including: child's name, age (DOB), gender, preferred language, assigned primary care provider, parent's name, and phone number as well as the date of their upcoming well child check.

Procedures

Recruitment, Screening, Consent, and HIPAA Authorization

Upon receipt of the patient lists, the names will be entered into REDCap and the study team will call through the list in order until the quota for each of the four clinic systems, spread across 10 sites throughout Los Angeles County, is reached. When called, the RA will provide information about the study to each family / parent as well as provide them with an opportunity to ask questions. In addition, study flyers will be posted in each of the clinic system's waiting rooms. RAs will attempt to contact families up to 10 times - either by phone or by text during recruitment - unless additional contact is specifically requested by the family.

If a family is interested and elects to be screened for study eligibility, the RA will conduct the eligibility screening over the phone. The following eligibility criteria will be assessed during the screening process.

- 1) a parent or legal guardian who is at least 18 years of age,
- 2) a parent or legal guardian comfortable participating in the study in English or Spanish,
- 3) a child 11-42 months of age with an upcoming well child check,
- 4) a child scheduled for a 1- to 3-year old well child check-up (appointments are often scheduled early or late in comparison to child's actual age)
- 5) a child who is not receiving or has not received developmental or behavioral services,
- 6) a child who has not received a developmental or behavioral diagnosis, and
- 7) a child who has not been referred for developmental or behavioral services or evaluation.
- 8) Run-in phase (UCLA IRB #18-000465) study participants will also be excluded - this will be determined before a potential participant is called.
- 9) Children with a sibling currently or previously participating in this phase of the study will also be excluded - this will be reviewed by study record prior to calling the potential participant and will also be confirmed by the screening script.

If eligible, the RA will review the study with the family over the phone and obtain oral consent as well as offer to text or email the study information sheet. In addition, the RA will send via email or text (based on the family/respondent preference) a link to the UCLA External REDCap platform for each family to complete and sign electronically a HIPAA authorization form for research for medical record access to allow for later record review and abstraction. HIPAA authorizations forms completed electronically through the External REDCap platform, will be downloaded and provided to each clinic via secure fax, secure email, or printed in hard-copy - based on each clinic system's preferences. The process for obtaining HIPAA research

authorization at the participating clinics as outlined is acceptable and compliant with the participating clinic's HIPAA policies and procedures.

Baseline Data Collection – Developmental Screening

The RA will administer the age-appropriate screening survey over the phone using the peds-test-online, which includes the Modified Checklist for Autism in Toddlers, Revised (M-CHAT-R™) for children at least 16 months of age, the Parents' Evaluation of Developmental Status (PEDS), and the Parents' Evaluation of Developmental Status: Developmental Milestones (PEDS:DM). The peds-test online system scores parental responses to each of the administered questions and provided screening results for each of the individual instruments. Screening results will be provided verbally to each parent. An overall risk level will be calculated using all 3 measures – high risk will be defined as PEDS Path A or an M-CHAT-R failure, moderate risk will be defined as PEDS Path B or 3 unmet milestone on the PEDS:DM, low risk will include Path C and E with a passed M-CHAT-R and with 2 unmet milestones or fewer on the PEDS:DM.

Randomization:

Randomization will be stratified by developmental screenings result (high/moderate vs. low) as well as by clinic system, creating 8 groups that will be divided between the intervention and control groups to ensure even representation. To determine group assignment, the Research Assistant will enter the developmental screening result and clinic into REDCap, which will calculate the risk level as well as assign group. The Research Assistant will provide the participant with their group assignment at this time as well as describe briefly the intervention further for the intervention group. In addition, the Research Assistant will remind the participant that a summary of the results will be provided to their doctor.

Baseline Developmental Assessments:

The Research Assistant will then administer two developmental assessments over the phone: the Child Behavior Checklist (CBCL) and the PEDS:DM-Assessment Level (AL). The subdomains of the CBCL the RA will administer include: attention problems, aggressive behavior, autism spectrum problems, and oppositional defiant problems. All children will be asked all CBCL questions. The PEDS:DM-AL includes several subscales: fine motor, self-help, receptive language, expressive language, gross motor, social emotional, and academic. Together, they combine to form the cognitive overall score, which is used to calculate age equivalency. All low risk kids will receive the expressive and receptive language scale questions. Moderate and high risk kids will receive the full PEDS:DM-AL.

In addition, the RA will ask about families' experiences with care at the clinic and anticipatory guidance received; sociodemographic questions, including covariates such as child gender, parent education level, parent marital status, race/ethnicity, language, household composition and income, health insurance status, as well as a hunger scale and the PHQ2; a financial wellbeing scale, and the protective factors survey.

Engagement:

To keep families engaged and remind them of study participation over the 24-month period, parenting tips and child health information will be provided by text monthly – texts will be relevant to the full age range of the kids enrolled at any time point (11 months to 5 years) and will include topics such as sleep, screen time, safety, and nutrition. In addition, a reminder letter asking for updated contact information will be sent 1-2 months prior to each survey time point. A

text reminder will also be sent approximately 2 weeks before each follow-up data collection time point.

Study Conditions

Intervention:

Those in the intervention group will then be connected to 211LA via warm transfer phone call for care coordination, including a review of developmental screening responses and information about and connection to relevant developmental and behavioral evaluations and services. The care coordinator specialist will stay in touch with the family for 3-6 months or until the parent wishes to discontinue contact or the child is enrolled in services. The RA will also text a 211LA flyer and contact information to the parent. The RA will provide participant contact information (child and parent name, phone number, address) and basic demographic information (child age, race/ethnicity, language preference, education, income, insurance status, household size) to the care coordination specialist via an online encrypted WebForm hosted on 211LA's HIPAA compliant care coordination platform / database.

After connection to 211LA, the care coordination specialist will develop a care coordination plan – including referrals suggested for community agencies – and will fax this plan to the clinic. At the conclusion of care coordination, the care coordination specialist will provide the outcome of each referral, including services received and barriers faced. This data will also be transferred to the research team via encrypted electronic transfer on an ongoing basis – along with care coordination time investment per participant.

After baseline data collection, parents will receive a \$25 cash incentive to compensate them for their time. This incentive will be mailed to study participants along with a copy of their HIPAA authorization and a copy of the study information sheet.

Measures

Follow-up Data Collection:

Participants will be contacted 3 more times after baseline for study research data collection – 6 months, 12 months, and 24 months after baseline. Follow-up data collection will be very similar to baseline data collection and parents will receive \$15, \$25, and \$25 cash incentives to thank them for their time. For hard-to-reach participants, we will add a small additional incentive of \$10 dollars in value at any time point (6M, 12M, 24M).

The 6-month survey includes the M-CHAT-R for children who were too young at baseline to receive the screening. No other developmental screenings will be administered at 6, 12, or 24 months. The Child Behavior Check List will be administered at 6, 12, and 24 months and the PEDS:DM-AL will be administered in the same fashion as baseline at 12 and 24 months, as will experiences with care and anticipatory guidance. At all follow-up time points, participants will be asked about referrals and connections to services and those in the intervention group will be asked about their experiences with 211 at 6 months. At each follow-up time point, the RA will call and text a study participant up to 20 times each (10 calls, 10 texts) to connect for the interview, unless otherwise specified by the family. We will contact by email study participants that we have already contacted by phone but haven't been able to reach to complete the follow-up surveys.

Chart Abstraction:

Medical record review will occur at baseline and throughout the study time period. The RA will conduct electronic health record reviews for each of the study participants. They will assess developmental surveillance, developmental screening (validated screening tool use), and documentation of referrals and services from birth to baseline as well as in the 24 months of the study period. After completing site-specific training and documentation, the RA will be provided with an administrative login for each site's electronic health / medical record. They will use this to log in to access the electronic medical record and review the study participant's record for the noted elements. In addition, the RA will review for process measures – including the attendance of the scheduled baseline well child check-up, upload of developmental screening results into the medical record, as well as upload of the care plan and care coordination outcome summary.

Statistical and Data Analysis Plan:

Given that the intervention being tested requires parent adherence to recommendations (e.g., communicating with 211LA, keeping referral and service appointments) to achieve success, we will use an intention-to-treat analysis. Our analyses will be based on measuring differences between the intervention and comparison groups with respect to the above outcome variables. Additionally, covariate-adjusted differences will be evaluated using multivariable regression models. Incomplete variables will be handled using a multiple imputation approach with 10 imputations for multivariable analyses; imputations will be based on an iterative Markov chain Monte Carlo method, with initial values generated by an expectation–maximization algorithm. Finally, secondary analyses for all outcomes will include group*developmental screening risk category (low, moderate, high), or group*gender (female, male) interactions to explore differential intervention effects.

Hypothesis 1: A higher proportion of families in the intervention group will a) be successfully referred to early childhood service organizations for evaluation, and b) receive services, than families in the usual care group.

We will use multivariable logistic regression models for each of these binary outcome variables with group assignment as the main predictor, controlling for socio-demographic variables.

Secondary analyses will use the fact that multiple types of services may be indicated. This will allow us to examine specific services in isolation as binary outcome variables in logistic regressions. It is possible that certain types of services are more likely to be recommended or taken up than others. It is also possible that receipt of any vs. no services is too crude to distinguish among different types or severities of developmental needs. Thus, examining specific services may prove to be important adjunct analyses.

Hypothesis 2: Over time, formal developmental assessment scores in the intervention group will improve more than scores in the usual care group.

In all children, linear regressions will be used to compare PEDS:DM-AL language subscale scores in each arm. In the subset of children who screened positive and therefore received the full PEDS:DM-AL (Parents' Evaluation of Developmental Status: Developmental Milestones - Assessment Level), linear regressions will be used to compare each of the subscale scores in each arm. Since we will have baseline and 2-year follow-up PEDS:DM-AL scores, we will use change from baseline scores as outcomes, allowing us to compare change in the intervention group against change in the comparison group.

We will also conduct exploratory secondary analyses, each with probative value but less certain power. Since we will have scores measured at baseline and 1-year and 2-year follow-ups, we will be able to conduct longitudinal analyses, with multiple observations clustered within individuals using linear mixed models with random child effects. These models will adjust for

socio-demographic variables. The outcome variables will be appropriately transformed prior to fitting the model as needed.

The mixed effects models described above allow us to make statistical inference using all observed data, with the assumption of data missing at random. To assess the robustness of this analysis with respect to missing data, multiple imputation with pattern mixture models will also be used to impute missing data due to missed visits or loss to follow-up. For example, as a sensitivity analysis, we will assume that the distribution of missing data from missed visits or loss to follow-up is similar with that of the usual care group.

Secondary outcomes will include CBCL, family-centered care, and satisfaction scores. We will conduct longitudinal analyses like those for the language subscales. Also, sensitivity analyses clustering children by provider will be performed to assess robustness of findings to potential contamination by provider.

Hypothesis 3: Intervention costs per child screened will be exceeded by the societal value of the long-term benefits from 211-based care coordination.

We will compare costs per child screened to benefits. Total costs will be disaggregated into RA screening/initial referral, 211 program, and diagnostic and developmental services costs. Total benefits will be disaggregated into income and value of life expectancy gains. Using evidence from literature, these benefits will be estimated by predicting changes in educational achievement from improvements in early life assessments (Aim 2 findings), then predicting changes in educational attainment from changes in educational achievement, and then predicting changes in lifetime income and life expectancy from changes in educational attainment. Sensitivity analyses will explore alternative assumptions about costs, relationships between early-childhood development and long-term outcomes, and value of a life-year.

Power Analysis

Given our planned RCT enrollment of 662 families (331 per group), and assuming loss to follow-up of 20% per year, we expect 424 families (212 per group) to complete the study. For each hypothesis, we report minimally detectable differences using study completers. These estimates are likely conservative, since some analyses will be performed using data collected prior to the end of follow-up and including >424 families. The enrollment sample size was chosen so that detectable differences would be within the bounds of the confidence intervals from the pilot data. Unless otherwise noted, reference rates were estimated from the pilot study.

Hypothesis 1: A higher proportion of families in the intervention group will a) be successfully referred to early childhood service organizations for evaluation, b) be deemed eligible for services by service organizations, and c) receive services, than families in the usual care group.

a) A sample size of 212 per group provides 80% power to detect a 11.9 percentage-point difference in the referral rate, assuming a reference rate of 20.4%, a chi-squared test, and an alpha of 0.05. This difference is smaller than observed in the pilot study (21.8 percentage points; 95% CI: 9.1-33.8).

b) A sample size of 212 per group provides 80% power to detect an 9.2 percentage-point difference in the eligibility rate, assuming a reference rate of 8.6%, a chi-squared test, and an alpha of 0.05. This difference is smaller than observed in the pilot study (14.3 percentage points; 95% CI: 5.6-24.0).

c) A sample size of 212 per group provides 80% power to detect a 8.7 percentage-point difference in the service receipt rate, assuming a reference rate of 7.2%, a chi squared test, and an alpha of 0.05. This difference is smaller than observed in the pilot study (11.7 percentage points; 95% CI: 3.4-21.0).

Hypothesis 2: Over time, formal developmental assessment scores in the intervention group will improve more than scores in the usual care group.

Meta-analyses of interventions studies have shown a range of effect sizes (Cohen's d), from 0.3-0.8 for speech and language therapies, and 0.3-1.19 for Autism Spectrum Disorder. A sample size of 212 per group provides 80% power to detect an effect size as small as 0.27 on the PEDS:DM-AL, assuming a two-sample t-test, and a two-sided alpha of 0.05.

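### The baseline PEDS:DM-AL, CBCL and experience-of-care items follow disclosure of the group, so the baseline in the Hypothesis 2 change score cannot be assumed independent of allocation

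*Combined protocol and SAP*

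**What the plan says.** All references are to the combined protocol and SAP.

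- **Before allocation.** Under Baseline Data Collection – Developmental Screening, the parent answers the PEDS, the PEDS:DM and, for children of at least 16 months, the M-CHAT-R, and hears the results.
- **Allocation and disclosure.** Under Randomization, a single REDCap step calculates the risk level and assigns the group. Then: "The Research Assistant will provide the participant with their group assignment at this time as well as describe briefly the intervention further", the description being for the intervention group.
- **Baseline scales.** Under Baseline Developmental Assessments: "The Research Assistant will then administer two developmental assessments over the phone", namely the CBCL and PEDS:DM-AL. Risk level decides how much of the latter is asked: "All low risk kids will receive the expressive and receptive language scale questions", while moderate- and high-risk children get the full instrument. Experience-of-care questions and the sociodemographic survey are listed next.
- **Analysis.** Under Hypothesis 2 of the analysis plan: "In all children, linear regressions will be used to compare PEDS:DM-AL language subscale scores in each arm". The other subscales are compared "In the subset of children who screened positive and therefore received the full PEDS:DM-AL". For these comparisons, "we will use change from baseline scores as outcomes". The baseline is also one of the time points in the longitudinal models. In addition, "Secondary outcomes will include CBCL, family-centered care, and satisfaction scores".
- **Follow-up.** The same parents report again at 12 and 24 months (CBCL also at 6 months), and "those in the intervention group will be asked about their experiences with 211 at 6 months".

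No section delays disclosure, describes a blinded assessor, or plans an analysis that avoids the post-disclosure baseline.

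**The concern.** Randomization makes the arms comparable on anything measured before allocation. It gives no such protection to a parent-reported score taken just after the parent learns the group, by a Research Assistant who also knows it. A parent who expects help may describe the child's difficulties more fully, or less so; a parent assigned to usual care may also answer differently.

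This matters most for Hypothesis 2, because a change score subtracts the baseline with a coefficient of 1. Hypothesis 3 inherits the result, since its benefit model starts from the Aim 2 findings. The CBCL is exposed in its secondary longitudinal analysis. So are the experience-of-care items, if they supply the family-centered care and satisfaction scores.

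There is also a completeness issue. A parent who ends the call on hearing the group has been randomized but has no baseline on these scales, and this could happen more often in one arm.

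**Working it through.** **1. The plan's own figure.** Power Analysis: 662 × 0.8 × 0.8 = 423.7, stated as 424 completers, or 212 per group. The detectable effect is (1.960 + 0.842) × √(2/212) = 0.272, which agrees with the stated 0.27. That figure is not in dispute; it only gives a scale.

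**2. How a reporting shift enters.** Let d0 and d24 be the between-arm differences in reporting caused by knowing the group, at baseline and at 24 months, in SD of the raw score. With no true effect:
- current order: bias in the change score = d24 − d0;
- scales collected before allocation: d0 = 0, so bias = d24.

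The documents give neither quantity. d24 = 0 cannot be presumed, because by then intervention parents have been offered 3-6 months of care coordination, have been asked about 211 at 6 months, and report with no described blinding.

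**3. Illustration of size.** Assumed: correlation ρ between baseline and 24-month score of 0.3, 0.5 or 0.7, and equal SDs. From the plan: n = 212 per arm and two-sided alpha 0.05.

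SE = √(2(1 − ρ)) × √(2/n) = 0.115, 0.097, 0.075.

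Rejection rate = Φ(−1.96 + |bias|/SE) + Φ(−1.96 − |bias|/SE). For ρ = 0.5 and bias 0.10: 0.10/0.0971 = 1.03, giving Φ(−0.93) + Φ(−2.99) = 0.18.

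| Net bias (SD) | ρ = 0.3 | ρ = 0.5 | ρ = 0.7 |
|---|---|---|---|
| 0 | 0.050 | 0.050 | 0.050 |
| 0.05 | 0.072 | 0.081 | 0.102 |
| 0.10 | 0.140 | 0.177 | 0.265 |
| 0.15 | 0.257 | 0.339 | 0.513 |

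These rates apply to the language subscales in all children. The other subscales use the screen-positive subset, whose size is not given. If it were 40% of completers (85 per arm), a net bias of 0.10 SD would give 9-13%.

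**4. Does collecting the scales earlier reduce the bias?** Only if |d24| < |d24 − d0|, that is, d24 < d0/2 when d0 > 0. With d0 = 0.10:

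| d24 | Type I error, current order | Type I error, scales before allocation |
|---|---|---|
| −0.05 | 26-51% | 7-10% |
| 0 | 14-26% | 5% |
| 0.05 | 7-10% | 7-10%, sign reversed |
| 0.10 | 5% | 14-26% |

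**5. What the remedial analyses can show.** A baseline comparison at 331 per arm has SE √(2/331) = 0.078, a 95% half-width of 0.15 SD, and about 25% power for a 0.10 SD shift. The 24-month score adjusted for pre-randomization screening has SE √(1 − r²) × √(2/212) = 0.097, 0.084, 0.069 for an assumed screening-to-outcome correlation r of 0, 0.5, 0.7. That compares with 0.115 to 0.075 for the change score, so precision need not suffer.

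**The case against.** The exposure is limited. Parents in both arms have already answered the screening questions and heard the results, and only knowledge of the group and a brief description come between. The 211LA warm transfer is described later, under Study Conditions. All of this stands, and it is why the point is minor. A reader might infer that care coordination has begun before the baseline; the documents do not say so.

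A reader might also infer that the baselines do differ by arm, or that Hypothesis 2 is biased toward the intervention. Nothing supports either reading. The order leaves independence unprotected; it does not disprove it. The net effect could favour the intervention, mask a benefit, or cancel.

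On missing baselines, a reader might think the plan has no answer. It has a partial one: intention-to-treat analysis, multiple imputation with 10 imputations for multivariable analyses, mixed models under missing at random, and a pattern-mixture sensitivity analysis for missed visits or loss to follow-up. These do not exclude baseline missingness related to the arm.

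The strongest objection is that the remedy may not reduce bias. If the same reporting shift persists to 24 months, the present order cancels it and the new order does not. The algebra is right. But the plan cannot verify that two unmeasured biases cancel, whereas a baseline taken before allocation is free of d0 by design. It is also fair that the fallback analyses have limited power, and that every error rate above rests on assumed shifts and correlations.

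**Conclusion.** The point holds as a minor design weakness. The order is explicit for the PEDS:DM-AL and CBCL, and the experience-of-care items are listed after them. These parent-reported baselines cannot be assumed independent of allocation, and for the PEDS:DM-AL any shift d0 passes in full into the Hypothesis 2 estimate as d24 − d0. Size and direction are unknown. The ranges of 7-10% for a net bias of 0.05 SD and 14-26% for 0.10 SD illustrate sensitivity at 212 per arm for assumed correlations of 0.3 to 0.7; they do not estimate this trial's error rate. Hypothesis 1 outcomes use no baseline score and are unaffected.

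**What to change.** **If enrollment is open** (the documents do not say): split the REDCap step. Calculate the risk level first, since it decides between the full and language-only PEDS:DM-AL. Administer the PEDS:DM-AL, CBCL and experience-of-care items, then generate and disclose the assignment. The sociodemographic and other survey items need not move. The justification is a baseline measured before allocation and available for every randomized child. It is not a guaranteed fall in net bias, because a shift that persists to 24 months is no longer offset.

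**For children enrolled under the current order:**
1. Report these baseline scores and their completeness by arm with confidence intervals, and do not read a non-significant difference as no shift.
2. Add a Hypothesis 2 sensitivity analysis of the 24-month PEDS:DM-AL score, adjusted for age, clinic system and the pre-randomization PEDS, PEDS:DM and M-CHAT-R results instead of the post-disclosure baseline. Use a not-applicable M-CHAT-R category for children under 16 months; their 6-month M-CHAT-R comes after allocation and should not be substituted. State in advance that agreement means the conclusion does not depend on the post-disclosure baseline, and that disagreement shows sensitivity to it without identifying the cause.
3. State as a limitation that follow-up reporting bias (d24) remains.

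**Cost:** one reordered phone script, one REDCap form split in two, and two short analyses of data already planned. The longer step before randomization may lose some families, which would also reduce the number available for Hypothesis 1; the documents give no figure for this. If enrollment is closed, only the analyses and the stated limitation apply.

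### Ten imputations leave a borderline adjusted 24-month result partly dependent on the random seed, given about 36% expected loss; raising the number is a free, minor improvement

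*Combined protocol and SAP*

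**What the plan says.** The Statistical and Data Analysis Plan calls for an intention-to-treat analysis with covariate-adjusted regression models. Incomplete variables are handled by a "multiple imputation approach with 10 imputations for multivariable analyses", using Markov chain Monte Carlo. It gives no reason for 10, no seed and no Monte Carlo error criterion.

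The Power Analysis starts from 662 enrolled families and says: "assuming loss to follow-up of 20% per year, we expect 424 families (212 per group) to complete the study". It adds: "For each hypothesis, we report minimally detectable differences using study completers". It also gives a caveat: "These estimates are likely conservative, since some analyses will be performed using data collected prior to the end of follow-up".

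Under Hypothesis 2, the main analysis is a linear regression of change from baseline to 2 years in PEDS:DM-AL scores. Exploratory mixed models use all observed data. A pattern-mixture imputation, with no number of imputations stated, checks the robustness of those models to missed visits and loss to follow-up.

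**The concern.** A small number of imputations is usually defended on average efficiency, and on that measure 10 costs little. A second cost is easier to overlook. The pooled estimate, its standard error and its p-value all depend on the random draws, and that dependence grows with the information lost to missing data. With about a third of 24-month outcomes missing and no seed fixed, two analysts following the same plan on the same data could report different p-values. For a result close to 0.05 they could fall on opposite sides of it. The stake is reproducibility of a borderline adjusted result, with a small loss of power.

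**Working it through.** **Inputs.** From the documents: m = 10 imputations (Statistical and Data Analysis Plan); 662 enrolled, 20% loss per year, 424 completers, 80% power (Power Analysis); two-sided alpha 0.05 (Power Analysis, Hypothesis 2). Assumed, because the documents give no value: FMI of 0.20 to 0.36, with 0.10 as a favourable case. The value 0.36 sets FMI equal to the share missing. It would be lower if baseline and earlier follow-up data predict the outcome.

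**1. The plan's own figure.** 662 × 0.8 × 0.8 = 423.7, so 424 completers reproduces. Share missing at 24 months: 1 − 424/662 = 0.36. The recruitment target of 685 in the abstract's Methods gives the same share (685 × 0.64 = 438), so the difference between 662 and 685 does not matter here.

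**2. Simple formula.** In units of the standard error, the Monte Carlo SD of the pooled estimate is √(FMI/m). For a result at z = 1.96, the 95% range over seeds is 1.96 ± 1.96 × √(FMI/m).

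- FMI 0.36, m = 10: √0.036 = 0.190; z from 1.59 to 2.33; p from 0.112 to 0.020.
- FMI 0.36, m = 50: √0.0072 = 0.085; z from 1.79 to 2.13; p from 0.073 to 0.033.

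The average inflation of the standard error at m = 10 is only √(1 + 0.36/10) = 1.018, or 1.8%.

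**3. Full Rubin's rules.** The simple formula holds the standard error and degrees of freedom fixed. Letting them vary by simulation widens the ranges. All rows are for a result that would be p = 0.05 with unlimited imputations.

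| FMI | m | Simple formula, 95% range of p | Full Rubin's rules, 95% range of p | Full Rubin's rules, middle half of seeds |
|---|---|---|---|---|
| 0.36 | 10 | 0.020–0.112 | 0.015–0.150 | 0.037–0.082 |
| 0.20 | 10 | 0.025–0.092 | 0.023–0.109 | 0.040–0.069 |
| 0.10 | 10 | 0.031–0.078 | 0.030–0.084 | 0.043–0.061 |
| 0.36 | 50 | 0.033–0.073 | 0.030–0.082 | 0.043–0.061 |
| 0.36 | 100 | 0.038–0.065 | 0.035–0.071 | 0.045–0.057 |

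**4. Direct check.** One simulated data set (331 per arm, 212 observed per arm) was imputed repeatedly with 10 imputations, changing only the random draws. The 95% range was 0.015–0.157 without an auxiliary variable (FMI 0.355). It was 0.023–0.110 with an auxiliary variable correlated 0.7 with the outcome (FMI 0.22).

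**5. How often a decision changes.** Take 80% power with unlimited imputations, so that z is centred on 1.96 + 0.84 = 2.80, and FMI 0.36. The comparison is with the decision that unlimited imputations would give.

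| m | Decision differs | Power |
|---|---|---|
| 10 | about 6.7% of trials | about 77% |
| 50 | about 2.6% of trials | about 79% |

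Type I error stays at 0.05. For a data set whose result sits exactly at z = 2.80, the 95% seed range with m = 10 is p = 0.001 to 0.035, and about 0.6% of seeds cross 0.05.

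**The case against.** **The 10 imputations may not cover lost outcomes.** The rule follows directly on the sentence about covariate adjustment, and loss to follow-up has its own pattern-mixture imputation under Hypothesis 2. If only covariates are imputed, FMI for the treatment effect would be small and the point would nearly vanish. This reading is possible but not the natural one. The rule speaks of incomplete variables without limiting them to covariates, in an intention-to-treat analysis, and the pattern-mixture step is a sensitivity analysis for the mixed models. What stands is that the point is conditional on outcomes being imputed.

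**The 36% does not fit every outcome.** A reader might apply it to Hypothesis 1 as well. The documents do not support that. Referrals and services are asked about at 6, 12 and 24 months and abstracted from medical records over the 24 months, and 211LA reports referral outcomes for the intervention arm. A recorded referral is not lost when the 24-month call is missed. The Power Analysis itself says that some analyses will include more than 424 families. This objection stands.

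**The wide range is a conditional extreme.** A reader might infer that any reported p-value will swing between 0.02 and 0.11. That is a 95% range for a result exactly at the threshold, under an assumed FMI. Most seeds give much less movement, and results well away from 0.05 keep their conclusion.

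**More imputations do not cure it.** With 50, a boundary result still ranges over about 0.03 to 0.07 by the simple formula. A recorded seed makes the reported result repeatable at any number of imputations, but it does not reduce the Monte Carlo error in that result. Both are therefore needed.

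**Conclusion.** The point holds as a minor, free improvement. It rests on three conditions: missing 24-month outcomes are imputed under the 10-imputation rule; FMI is about 0.20 to 0.36, which is an assumption; and the result lies near 0.05. Under them the 95% seed-to-seed range of p is about 0.02 to 0.11, wider under full Rubin's rules at the top of the FMI range. At FMI 0.10 it narrows to about 0.03 to 0.08. The 6.7% of changed decisions and the three points of lost power belong to FMI 0.36, the upper end of the assumed range, and would be smaller below it.

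The point applies most directly to the covariate-adjusted 24-month PEDS:DM-AL change scores. It may apply less to referral and service receipt. It does not touch the mixed models fitted to observed data, which do not depend on the number of imputations.

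A reader might infer that the planned tests are biased or invalid. They are not, because type I error stays at its nominal level with 10 imputations.

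**What to change.** In the Statistical and Data Analysis Plan, change 10 imputations to at least 50; 100 is also trivial to run. Prespecify and record the seed, and report the Monte Carlo error of the main adjusted estimates. One added sentence should say whether missing outcomes, and not only covariates, are imputed under this rule. The cost is one number, one or two sentences and minutes of computing, with no new data or participants. Seed dependence is reduced, not removed: at FMI 0.36, 100 imputations still leave a boundary result at about 0.035 to 0.07 under full Rubin's rules. The reported Monte Carlo error lets readers see how much remains.
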